6. STUDY PROCEDURES AND ASSESSMENTS

6.1. Phase I – Pre-STSG

6.1.1. Day 0 – Screening Visit and Informed Consent

6.1.1.1. Informed Consent

Prior to conducting study activities, written consent will be obtained from all participating subjects and documented on an informed consent form (ICF) that has received approval by an IRB/Ethics Committee. The ICF must be written in adherence to Good Clinical Practice (GCP) and comply with all elements required by FDA CFR 50.25 and International Conference on Harmonization (ICH) 4.8, state and local regulations, and additional elements relevant to specific study situations, (including a statement that Medline Industries, Inc. and authorities have access to subject records). A copy of the signed consent form will be given to each participating subject.

6.1.1.2. Eligibility Screening

Potential participants will be screened for eligibility via a combination of the screening form, provided separately by Medline Industries, Inc., and by a review of the potential participant's burn wound and medical chart by one of the site investigators or their staff. In the event a participant has multiple burn wounds, the site investigator will select the target wound that meets the inclusion criteria; in the event more than one wound meets all inclusion criteria, the site investigator will choose the wound (target wound) he or she believes to be most clinically appropriate for treatment with the device. If a potential participant with diabetes does not have an A1C level recorded in his or her chart within the past 90 days, a qualified member of the study staff or a site investigator's institution will perform a blood draw to be used for A1C calculation. If a potential participant has NPWT on the target wound during screening, that participant may still be included in the study provided that participant meets all the inclusion criteria, none of the exclusion criteria, and if NPWT will be discontinued right before application of the device.

6.1.2. Day 1 – Initial Visit

6.1.2.1. Demographics, Comorbidities, Wound history and Medication

To allow for a deeper understanding of the effect of the device on patients' wounds, demographic information, patient co-morbidities, historical treatment modalities of the target wound, and current medication list will be collected at the time of initial visit. Intake of analgesics will be captured throughout the study. Information pertaining to the escharectomy procedure will also be recorded. This will allow for post-hoc analyses that may inform the design of the larger clinical study. Information will be recorded on the Case Report Forms (CRFs) provided separately by Medline Industries, Inc.

6.1.2.2. Wound Photograph and Area Measurement

During the initial visit, a member of the study staff will take a photograph of the wound using a specialized wound camera with image analysis software (inSight® by eKare Inc.), postescharectomy and immediately prior to application of the device. The image analysis software will calculate wound volume and area automatically, and will collect wound depth. In the event the camera or software malfunction, wound area and volume will be assessed manually with a ruler or other measuring device used for measuring wound area and volume.

6.1.2.3. Pain Assessment

Patients will be asked to rate their current level of pain, both overall and at the wound, using a verbal Likert-type scale. Patients will respond with a whole number between 0-10, with 0 corresponding to "no pain" and 10 corresponding to "the worst pain imaginable."

6.1.2.4. Analgesic Usage

Since usage of analgesic(s) will likely affect a patient's self-assessment of pain, analgesic usage will be recorded throughout the study in order to provide a full picture of pain management. This information will be recorded on CRFs provided separately by Medline Industries, Inc.

6.1.2.5. Infection Evaluation

At this visit, as well as all visits and during the continuum of the patient's participation in the study, the wound site will be evaluated for the development of an infection. In the event of a suspected infection, clinical staff will collect a wound culture. Should a patient develop an infection, this will be noted as an expected adverse event (AE) and the participant's participation in the study will be terminated.

6.1.2.6. Placement of the device

After taking wound photograph (post-escharectomy), conducting wound area and volume measurement and assessment, the site investigator or qualified study staff will place the

A clinical evaluation of an esterified hyaluronic acid matrix on preparing wounds in burn patients for split-thickness skin grafting

MED-2018-DIV31-006

V2.0

CONFIDENTIAL

device on the wound, along with an appropriate secondary dressing. Wound photograph will also be taken immediately after application of the device.

6.1.3. Interim Visits – Day 7, 14, 21, 28, 35, 42

At the interim visits during Phase I, patients will have their wound assessed, and will then be photographed using the same method as described in section 6.1.2.2. Remaining Interim visit activities will then be performed as stated in 6.1.2.3 through 6.1.2.5. The site investigator will assess if the wound is ready to receive an STSG at these visits. If the wound is ready for an STSG, the date of STSG approval and planned date of STSG procedure will be noted on the CRF provided by Medline Industries, Inc.. Should the site investigator deem that healing has progressed such that an STSG is no longer necessary, the patient's participation in the study will be discontinued. If after 21 days of device usage the patient is not ready to receive an STSG, a second application of the device may be applied and Phase I will be extended for an additional 21 days (for a maximum of 42 total days of device usage). If the patient is unwilling or clinically inappropriate, per determination by the PI, to receive a second application of wound matrix or STSG after 21 days, the patient's participation in the study will end. Alternatively, if the site investigator believes the wound will be ready to receive an STSG within three additional days of healing, but does not require another device application, the silicone backing of the device will be removed at Day 21 and the STSG will be scheduled by the Investigator or treating physician. Similarly, after 21 days of second application of the device, if the site investigator believes the wound will be ready to receive an STSG within three additional days of healing, the silicone backing of the device will be removed 21 days after the second application of the device and the STSG will be scheduled by the investigator or treating physician. STSG will be scheduled by the investigator or treating physician. Information pertaining to length-of-stay and discharge will also be collected. The timing of the visit days is approximate, as scheduling challenges may cause the exact visit days to not occur exactly every seven days. However, visits should occur within +/- two days of the original sevenday interval.

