3. OBJECTIVES AND ENDPOINTS

OBJECTIVES	ENDPOINTS	JUSTIFICATION FOR ENDPOINTS
Primary		
Evaluate the capability of the device to prepare post-escharectomy wounds in burn patients to receive an STSG.	Number of days from initial application of the device to approval of wound to receive an STSG.	Marker of wound healing progress
Secondary		

A clinical evaluation of an esterified hyaluronic acid matrix on preparing wounds in burn patients for split-thickness skin grafting

MED-2018-DIV31-006

V2.0

CONFIDENTIAL

1. Evaluate clinical outcomes of burn patients 2. Health outcomes	(1a) Change in wound volume from the time prior to application of the device to the time before the application of STSG and after STSG (1b) Length-of-stay at inpatient unit (1c) Patient pain rating (1d) Proportion of STSG take for the wound at 28 days, per clinician judgement (1e) Proportion of patients who develop an infection of the target wound at any time, per confirmation with culture (2a) Length-of-stay as inpatient (2b) Type of care setting where patient is discharged	Common clinical endpoints to measure outcomes in wound management. Common analysis to determine cost-effectiveness of device usage.
----------------------------------------------------------------------	-------------------------------------------------------------------------------------------------------------------------------------------------------------------------------------------------------------------------------------------------------------------------------------------------------------------------------------------------------------------------------------------------------------------------------------------------------------------------------------------------------------------	--------------------------------------------------------------------------------------------------------------------------------------------

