6.2. Phase II – Post-STSG

6.2.1. Interim Visits – Post-STSG Days 7, 14, 21, 28,

Following the completion of the STSG procedure, the patient will attend up to four interim visits to monitor wound healing progress and percent take of the STSG. Also, at Day 7 visit, information relating to the graft procedure will be recorded on the Surgical Procedures CRF provided separately by Medline Industries, Inc. At each visit, a photograph of the wound will be taken and the site investigator will also determine the percentage of STSG take at each visit, which will be based on the clinical judgement. The patient will also rate current pain level (overall and at the target wound) in an identical fashion to Section 6.1.2.3. A patient's participation in Phase II of the study will continue for 28 days post-STSG or until the site investigator determines weekly care is no longer needed. To document wound healing completion, a photograph of the healed wound will be taken. In order to track the participant's overall outcomes, any returns to the operation

A clinical evaluation of an esterified hyaluronic acid matrix on preparing wounds in burn patients for split-thickness skin grafting

MED-2018-DIV31-006

V2.0

CONFIDENTIAL

room to treat the target wound, any additional inpatient stays, and the type of facility the patient goes to at discharge will be captured on the CRFs. The timing of the visit days is approximate, as scheduling challenges may cause the exact visit days to not occur exactly every seven days. However, visits should occur within +/- two days of the original seven-day interval.

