8.3. Statistical Analysis

Descriptive statistics, including measures of central tendency (mean or median), measures of variation (standard deviations, coefficients of variation) and 95% confidence intervals and interquartile ranges, as appropriate, for the data distribution will be calculated for all endpoints. Demographic and baseline characteristics will be assessed as above and additional statistical analyses may be conducted in an exploratory fashion, as appropriate, for the data distribution.

- Time (in days) from initial application of wound matrix to approval of wound to receive an STSG.
- Change in wound volume from the time prior to application of the wound matrix to the time before the application of STSG and after STSG
- Length-of-stay as an inpatient

A clinical evaluation of an esterified hyaluronic acid matrix on preparing wounds in burn patients for split-thickness skin grafting

MED-2018-DIV31-006

V2.0

CONFIDENTIAL

- Patient pain ratings
- Proportion of STSG take, per clinician judgement, for the wound at 28 days
- Proportion of patients who develop an infection of the target wound at any time, per confirmation with culture
- Type of care setting where patient is discharged

Healthcare economics outcomes will be explored by combining length-of-stay data (both phases) and the type of care setting where the participant is discharged, with standard costs, reimbursement codes and other relevant health economics economic factors.

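### Phase I interim pain is rated after the wound has been assessed and photographed, so endpoint 1c can include pain from wound handling

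*Combined protocol and SAP*

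**What the plan says.** Section 6.1.3 sets the order of a Phase I interim visit. First, "patients will have their wound assessed, and will then be photographed using the same method as described in section 6.1.2.2". Next, "Remaining Interim visit activities will then be performed as stated in 6.1.2.3 through 6.1.2.5". Those subsections are pain (6.1.2.3), analgesic use (6.1.2.4) and infection evaluation (6.1.2.5).

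Section 6.1.2.3 describes the item: "Patients will be asked to rate their current level of pain, both overall and at the wound, using a verbal Likert-type scale". The answer is a whole number from 0 to 10. In Phase II, Section 6.2.1 repeats it: "The patient will also rate current pain level (overall and at the target wound) in an identical fashion to Section 6.1.2.3". That section does not say whether pain comes before or after the photograph and the graft-take assessment.

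The synopsis and Section 3 give endpoint 1c only as a patient pain rating. Section 8.3 lists "Patient pain ratings" among the endpoints to be summarised descriptively. None of the three names the overall or the wound rating, a visit, or a change from Day 1.

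The Schedule of Activities (Section 1.2) marks pain at Day 1 and at the Phase I visits. Its Phase II column has analgesic use, photograph and graft take, but no pain.

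**The concern.** The item asks about pain now, and at Phase I interim visits now means after the wound has been exposed and examined. The recorded value is then the wound's pain between procedures plus whatever the visit itself has added. Section 8.3 has no term for that addition, and with a single arm there is no comparator in which the same addition would appear.

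Readers are likely to look at 1c for the course of pain under the device. The instructions for use in Appendix 11.1 say that local pain normally falls markedly in the first two weeks after application. Ratings taken after handling could hide such a fall. A Day 1 rating taken close to surgery could exaggerate one. Section 7.1 also counts significant increases in pain as adverse events. It does not tie them to the 0-10 rating, but a site may well use that rating when judging them.

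Unlike the choice between two recorded ratings, the moment of rating cannot be changed once the data are in.

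**Working it through.** The plan gives no figure to reproduce: 1c has no stated effect size, standard deviation or power, and Section 8.1 rules out hypothesis testing. The check sets the sections side by side.

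**1. Order at each type of visit**

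| Visit | Pain relative to wound handling | Source |
|---|---|---|
| Day 1 | Not stated | 6.1.2.2, 6.1.2.3, 6.1.2.6 |
| Phase I interim | After assessment and photograph | 6.1.3 |
| Phase II interim | Not stated | 6.2.1 |

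The order is explicit only for Phase I interim visits. On Day 1 the pain subsection sits between the photograph and device placement, but Section 6.1.2.6 names only the photograph and the wound measurement and assessment as coming before placement. Numbering alone does not fix the sequence.

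**2. How many ratings are affected.** Phase I interim visits are scheduled at Days 7, 14, 21, 28, 35 and 42. Footnote b of the Schedule of Activities says Phase I will mostly end by 21 days. With 20 patients and full attendance:
- Phase I ends at Day 21 for everyone: 20 × 3 = 60 ratings of each type.
- Everyone continues to Day 42: 20 × 6 = 120 ratings of each type.

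Under the stated order, every one of these follows handling.

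**3. What handling does to a summary.** Write the recorded rating at visit v as Y(v) = P(v) + h(v), where P(v) is pain before handling and h(v) is the addition from handling. This ignores the floor and ceiling of the scale.
- The mean at one visit moves by the mean of h(v).
- The difference between visits v and w is [P(v) − P(w)] + [h(v) − h(w)]. The second bracket vanishes only if handling adds the same amount at both.
- In a change from Day 1, the bracket is h(v) − h(Day 1), and h(Day 1) is undefined because the Day 1 order is not stated.

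The documents give no value for h. Purely as an assumption, h of 1 to 3 points would raise each interim mean by 1 to 3 points. If h were 1 at one visit and 3 at another, the trend between them would be off by 3 − 1 = 2 points.

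**4. Is h likely to be constant?** Section 6.1.3 has the silicone backing removed at Day 21 for some patients, and again 21 days after a second application. It does not place that removal before or after the pain rating. Handling can therefore differ between visits and between patients.

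**5. Which rating is exposed to other sources of pain?** The wound and overall ratings are separate items in both phases, and no section pools them.
- Non-target burns can affect the overall rating at any visit. Section 6.1.1.2 allows several burn wounds, and Section 5.1 allows a target just above 0.5% of TBSA within a total burn below 20%.
- A donor site for the study graft can exist only after the STSG, so it can affect only the Phase II overall rating. That a graft leaves a painful donor site is a clinical inference; the documents do not discuss it.
- The target-wound rating is not designed to capture either.

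**6. Are Phase II data collected?** Section 6.2.1 requires both ratings, while the Schedule of Activities shows none. A site working from the Schedule alone would not collect them.

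**The case against.** The best defence has four parts.

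First, a fixed order standardises the interim visits, so a constant handling effect would cancel between them. That is right if handling adds the same amount each time, but the Day 21 removal of the backing is a reason to doubt it. Cancellation does not help the mean at a single visit, or a change from a Day 1 rating whose order is not stated.

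Second, this is a descriptive case series without a comparator, so no change in pain could be attributed to the device in any case. That stands and limits the seriousness. A descriptive endpoint should still describe a known quantity.

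Third, the protocol does not say that 1c is resting pain, and analgesic use is recorded throughout. Both are true. But Section 6.1.2.4 does not tie analgesic timing to the rating, and the text shows no intention to measure procedural pain.

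Fourth, dressing removal before the rating is inferred from the need to see the wound; Section 6.1.3 mentions only assessment and photography. This is fair, and the extent of handling is unknown.

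Stronger readings are tempting but unsupported. A reader might infer that 1c necessarily blends overall, donor-site and target-wound pain. It does not, because the ratings are recorded separately and the plural in Section 8.3 is compatible with reporting each. A reader might also infer that Day 1 pain is rated during or straight after surgery. Section 5.1 allows escharectomy to precede enrolment, no section requires it on Day 1, and a verbal numeric answer needs an awake patient. A perioperative Day 1 rating is possible for some patients but is not prescribed.

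**Conclusion.** The concern holds for Phase I interim visits. Section 6.1.3 places a current-pain item after wound assessment and photography, so 1c can carry procedural pain at all three to six of those visits. The size is unknown: the documents offer no estimate, and the 1 to 3 points above is only an illustration. The conclusion rests on sites following the written order and on assessment and photography involving enough handling to hurt.

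Mixing with pain from other burns or a donor site is a risk only if the overall rating is reported as 1c, which the undefined endpoint leaves open. The mismatch between the Schedule of Activities and Section 6.2.1 is a plain inconsistency that decides whether Phase II pain is recorded. All of this is minor for a secondary, descriptive endpoint, but worth correcting because timing cannot be repaired later.

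**What to change.** - **Sections 6.1.3 and 6.2.1:** have pain rated first at each visit, before the dressing is removed or the wound is assessed or photographed.
- **Day 1:** state one rating point relative to wound handling, the same for all patients, and record whether and when escharectomy was done. Do not set the rating before that day's anaesthesia: patients excised the same day would then have a pre-escharectomy baseline and the others a post-escharectomy one. Where the Day 1 rating is perioperative, do not read change from Day 1 as a device effect.
- **Synopsis, Section 3 and Section 8.3:** define 1c as the target-wound rating, with the overall rating as supportive, and name the visits and the summary measure.
- **Schedule of Activities:** reconcile with Section 6.2.1 on Phase II pain.

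The cost is a small change in visit workflow, a few lines of text and a field for escharectomy timing if the case report form lacks one. No visit or instrument is added. Ratings already taken under the present order should be flagged, since they are not interchangeable with those taken before handling.

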6.2. Phase II – Post-STSG

6.2.1. Interim Visits – Post-STSG Days 7, 14, 21, 28,

Following the completion of the STSG procedure, the patient will attend up to four interim visits to monitor wound healing progress and percent take of the STSG. Also, at Day 7 visit, information relating to the graft procedure will be recorded on the Surgical Procedures CRF provided separately by Medline Industries, Inc. At each visit, a photograph of the wound will be taken and the site investigator will also determine the percentage of STSG take at each visit, which will be based on the clinical judgement. The patient will also rate current pain level (overall and at the target wound) in an identical fashion to Section 6.1.2.3. A patient's participation in Phase II of the study will continue for 28 days post-STSG or until the site investigator determines weekly care is no longer needed. To document wound healing completion, a photograph of the healed wound will be taken. In order to track the participant's overall outcomes, any returns to the operation

A clinical evaluation of an esterified hyaluronic acid matrix on preparing wounds in burn patients for split-thickness skin grafting

MED-2018-DIV31-006

V2.0

CONFIDENTIAL

room to treat the target wound, any additional inpatient stays, and the type of facility the patient goes to at discharge will be captured on the CRFs. The timing of the visit days is approximate, as scheduling challenges may cause the exact visit days to not occur exactly every seven days. However, visits should occur within +/- two days of the original seven-day interval.

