4.2. End of Study Definition

A patient's participation in the study may end at several critical points:

- The patient completes Phase II.

A clinical evaluation of an esterified hyaluronic acid matrix on preparing wounds in burn patients for split-thickness skin grafting

MED-2018-DIV31-006

V2.0

CONFIDENTIAL

- The patient's physician determines a STSG is no longer necessary.
- The patient is unwilling or clinically inappropriate, per determination by the Investigator, to receive a second application of the device or STSG. The silicone backing should be removed at 21 days but the decision to reapply the device or schedule the STSG may happen up to three days thereafter.
- The patient is not ready to receive a STSG after two applications of the device. The silicone backing should be removed 21 days after the second application of the device but the decision to schedule the STSG may happen up to three days thereafter.
- The patient develops an infection of the target wound at any time.
- The patient needs NPWT of the target wound after application of the device.

The end of the study will coincide with the issuance of a clinical study report that has been approved by Medline's Clinical Affairs Director.

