8.2. Populations for Analyses

An evaluable population will be used for all analyses, with the definition of evaluable depending on the Phase of the study. For Phase I, all patients with an initial visit and a final interim visit resulting in resolution of Phase I will be included. In Phase II, patients with data from any interim visits who also complete Phase II to resolution will be included in analyses for Phase II.

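### A patient who exits for infection or NPWT before the post-STSG Day 7 visit has no required confirmation of grafting and no take reading, and section 8.2 then leaves that patient out of endpoint 1d

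*Combined protocol and SAP*

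**What the plan says.** Before surgery, section 6.1.3 asks the site for two graft-related entries: "the date of STSG approval and planned date of STSG procedure will be noted on the CRF".

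After surgery, section 6.2.1 sets the time for documenting the procedure itself: "Also, at Day 7 visit, information relating to the graft procedure will be recorded on the Surgical Procedures CRF". Percent take is judged at the Phase II visits, of which Day 7 is the first, and "visits should occur within +/- two days of the original seven-day interval". The Schedule of Activities (section 1.2) has no column for the day of the STSG, no row for the graft procedure and no exit visit.

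Two of the exit conditions in section 4.2 can occur in the first days after grafting: "The patient develops an infection of the target wound at any time" and "The patient needs NPWT of the target wound after application of the device". For infection, section 6.1.2.5 adds that "this will be noted as an expected adverse event (AE) and the participant's participation in the study will be terminated".

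Section 8.2 defines the analysis set for the second phase: "patients with data from any interim visits who also complete Phase II to resolution will be included in analyses for Phase II". Endpoint 1d (section 3) is the proportion of STSG take at 28 days.

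**The concern.** Between surgery and the first Phase II visit the plan schedules no study entry about the graft, yet a patient can leave the study in that interval. For such a patient the required CRF entries do not distinguish an exit before grafting from an exit after it, because a planned graft need not take place. Nor is there any value, or stated reason for having none, to carry into the take endpoint.

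These omissions are not random. The patients concerned are those whose target wound became infected or needed NPWT within days of grafting. If take is summarised without them, the figure describes grafts that got past the early period, and a reader may take it to describe all grafts placed on wounds prepared with the device. In a series of 20, one or two such patients can move the mean visibly.

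**Working it through.** The plan gives no figure for this point: section 8.1 sets 20 patients without a calculation, and no early-exit rate or expected take appears anywhere. The check is therefore a trace through the sections, followed by an illustration on stated assumptions.

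**1. The interval.** Day 7 with a window of two days either way: 7 − 2 = 5 and 7 + 2 = 9. Graft documentation and the first take reading are due on post-STSG days 5 to 9. An exit before that visit falls in the gap.

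**2. What is on file for a patient who exits in the gap.**
- STSG approval date and planned STSG date: required (6.1.3).
- Infection, if that is the reason: an AE entry (6.1.2.5, 7.6). This shows the infection, not that a graft was placed.
- NPWT, if that is the reason: no AE entry is required for NPWT as such.
- Actual graft date and procedure details: no stated rule for a patient who leaves before Day 7.
- Percent take: no reading scheduled before Day 7 and none at exit.

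**3. Whether the patient enters the 1d analysis.** Section 8.2 asks for interim-visit data and for completion of Phase II to resolution. It does not define resolution. The synopsis and 6.2.1 end Phase II at 28 days or when regular or weekly care is no longer needed, so an infection or NPWT exit is most naturally not a completion. Even if exit were read as resolution, a patient who leaves before Day 7 has no take value to contribute. On both readings the patient is absent from 1d.

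**4. Possible size (illustration only).** Let *g* be the number grafted, *k* the early leavers, *t* the mean take in those who remain and *s* the mean take assigned to leavers.

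Mean over all grafted = [*t*(*g* − *k*) + *s k*] / *g*

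The reported mean, without the leavers, is *t*. The gap is (*t* − *s*) × *k* / *g*.

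Assume *g* = 18, *t* = 95%, *s* = 0:
- *k* = 1: 0.95 × 17/18 = 0.897
- *k* = 2: 0.95 × 16/18 = 0.844
- *k* = 3: 0.95 × 15/18 = 0.792

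With other numbers grafted (*t* = 95%, *s* = 0):

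| *g* | *k* = 1 | *k* = 2 | *k* = 3 |
|---|---|---|---|
| 20 | 90.3% | 85.5% | 80.8% |
| 18 | 89.7% | 84.4% | 79.2% |
| 16 | 89.1% | 83.1% | 77.2% |
| 12 | 87.1% | 79.2% | 71.3% |

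Zero take is the worst case. With *s* = 50% and *g* = 18 the means are (16.15 + 0.5)/18 = 92.5%, (15.2 + 1.0)/18 = 90.0% and (14.25 + 1.5)/18 = 87.5%. With *s* = 95% there is no gap.

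**5. What produces the gap.** The formula has no term for when the procedure form is completed. The gap arises because leavers are removed (4.2, 6.1.2.5) and not counted (8.2). Completing the form on the day of surgery, with nothing else changed, would leave the reported mean at *t*.

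**The case against.** The strongest reply is that this is a matter of form completion in a descriptive case series with no hypothesis test. Four stronger readings that a reader might infer do go too far.

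- **That these patients leave no trace of a graft.** The approval and planned dates are on the CRF, an infection is on an AE form, the monitor has access to medical records (9.2.1) and verifies CRFs against source (9.2.3), and nothing bars completing the graft form later from the chart. The CRFs are supplied separately, so an exit form that captures graft status may exist. What is missing is a required confirmation.
- **That early graft failures drop out.** Graft loss is not an exit condition in 4.2. A patient who loses the graft without infection or NPWT stays in the study and has take assessed at Day 7.
- **That the main device result is flattered.** The primary endpoint stops at approval for STSG and is untouched. No listed endpoint counts grafted patients.
- **That the Day 7 timing inflates take.** Step 5 shows that it does not.

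All four replies stand. What they leave is narrower. A planned date does not establish that surgery occurred, and no section tells the site what to enter when a patient exits before Day 7. The plan as written would still report 1d without these patients. Correcting 8.2 alone would not be enough either, because a summary over all grafted patients needs a required record of who was grafted and an outcome or reason at exit.

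**Conclusion.** The point holds in a limited form. A patient who exits for target-wound infection or NPWT between the STSG and the first Phase II visit has no required confirmation of grafting and no take reading, and section 8.2 leaves that patient out of the take analysis. Endpoint 1d is then conditional on having avoided early infection or NPWT. If leavers' take is lower than that of the others, the reported figure is too favourable.

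The size cannot be derived from the documents. The drop from 95% to between 90% and 79% rests on three assumptions: 18 patients grafted, 95% mean take in those who remain, and zero take in 1 to 3 leavers. It shrinks as leavers' take approaches that of the others and is nil if nobody exits early. It measures the effect of the exit and completer rules together. This is a worthwhile, inexpensive improvement to a secondary endpoint; it does not threaten the primary result.

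**What to change.** - **Section 6.2.1 and the Schedule of Activities:** require the actual STSG date on the Surgical Procedures CRF for every grafted patient, entered at the procedure or from the operative note, whether or not the Day 7 visit takes place.
- **Any early exit from Phase II:** record at the exit contact the percent take, or that the graft was lost or could not be assessed, together with the reason for exit.
- **Sections 8.2 and 8.3:** report 1d with all grafted patients as the denominator, list early exits by reason, and give a sensitivity range for their take (for example from zero to the completer mean). Show the completer result alongside.

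The three parts belong together: the first two supply the data, and only the third changes what is reported. None of them alters the exit rules. The cost is one exit entry per early leaver and a small change to the schedule, with no new visit or assessor. The reported take may be less favourable.
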